### **A. Objective**

Roche Cobas Liat Flu/RSV POC Assay and procalcitonin testing as part of a stewardship intervention optimizes antiviral treatment and reduces antibiotic treatment for ED patients (under 50 years of age) with suspected influenza or RSV v. standard care using a prospective, patient-randomized design. In addition to the primary outcome, we will evaluate secondary outcomes including aggregate physician adherence to CDC guidelines for the treatment of influenza, antibiotic duration, hospital admission, and emergency department (ED) return visits within 30 days for patients diagnosed with influenza and RSV. Additional secondary outcomes would include time to resolution of symptoms, return to school/work, and subsequent healthcare utilization (e.g. doctor visits) obtained through patient self-report.

Hypothesis: The rapid waived POC assay and procalcitonin, as part of a stewardship intervention will lead to reduced antibiotic treatment by 20 percentage points compared to the control group for antibiotic non-responsive conditions including ILI and nonspecific URI and will increase appropriate antiviral treatment of patients with influenza at high risk recommended to receive treatment by 20 percentage points.

### **B. Background and Significance and Preliminary Studies**

Influenza and Respiratory Syncytial Virus (RSV) impose a serious disease burden in terms of morbidity and mortality. In the US alone, these illnesses are estimated to contribute to mean annual 51,203 and 17,358 deaths, respectively. RSV infections are estimated to result in approximately 1 of 334 all hospitalizations in children under the age of 5 years each year in the U.S. There is no effective antiviral treatment for RSV, and nosocomial RSV outbreaks are mainly controlled by isolation of infected cases, indicating the need for rapid diagnosis. Those especially at risk of complications from influenza include children who are under 2 years of age, adults 65 years or older, and those with immune suppression and underlying cardiopulmonary disease. Antiviral treatment has been shown to decrease risks of influenza-related complications in both of these age groups, with treatment most effective if administered within two days of diagnosis. However, previous lack of an accurate AND rapid point of care test for influenza makes prompt diagnosis of influenza a challenge, leading to significant over- and under-treatment with antiviral drugs.

The Centers for Disease Control and Prevention (CDC) currently recommend antiviral treatment for any patient with suspected influenza who is hospitalized or has severe or complicated illness. In outpatients, antiviral treatment is recommended for patients at high risk of

complications due to age or chronic medical conditions. However, the use of antivirals without any test result leads to not only unnecessary treatment, but also the risk of antiviral resistance. Furthermore, physician adherence to these guidelines is low, likely due to knowledge of these risks.

Antiviral under-treatment can be attributed to the poor sensitivity of current rapid diagnostic tools. For one, influenza-like illness (ILI) is defined by the CDC as the presentation of fever (temperature of 100°F [37.8°C] or greater) and cough or sore throat. These non-specific symptoms contribute to the low sensitivity and specificity of clinical diagnosis, which are approximately 64% and 67%, respectively. This sensitivity drops even further for those who meet the CDC criteria of patients at high risk for influenza-related complications. An observational cohort study found that the sensitivity of ILI reached only 31% for adult patients who met the CDC's criteria for antiviral treatment, likely due to these patients' dulled immune response. Thus, sensitivity of clinical diagnosis may be lowest for those who need antiviral treatment the most. Rapid influenza antigen tests are more specific, easy to use, and only take 15 to 30 minutes, but have a low sensitivity comparable to provider diagnosis. Procalcitonin has been demonstrated in multiple clinical trials to provide value in guiding antibiotic use particularly in respiratory infections for both adults and pediatric patients.

**Unfortunately fewer than 40% of patients who are recommended to receive treatment for influenza receive it in the ED. There are a variety of reasons for poor compliance with guidelines, including lack of awareness, poor understanding of the potential severity of influenza, and lack of accurate rapid diagnostic tests.** There is great potential for rapid, accurate PCR-based influenza and RSV testing to increase prompt antiviral treatment in high risk-patients, decrease antibiotic use in virally infected patients, and improve infection control. CLIA waived rapid, accurate testing could guide better diagnosis and management and improve patient outcomes.

### **C. Study Population**

**Inclusion criteria:** Patients <50 who are evaluated by the clinician for suspected influenza, including symptoms of ILI (fever >38°C and cough or sore throat) or non-specific URI for whom the clinician suspects RSV or influenza or lower respiratory infection (with or without ordering a chest xray).

**Exclusion criteria:** Patients who are pregnant, prisoners, or are unable to give informed consent in English or Spanish. Patients with influenza-like illness and upper respiratory symptoms for whom the provider is unwilling to wait for procalcitonin results.

**Sample size:** We plan to enroll 100 patients in each arm over a 12 month period (influenza season), which will have 80% power to detect a true 20 percentage point reduction in antibiotic use and 20 percentage point increase in adherence to guideline recommendations for antiviral treatment.

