#### **E. Study Endpoints**

[figure not shown]
The primary study endpoint is the determination of whether use of the Roche Liat Flu/RSV Assay and procalcitonin testing, as part of a stewardship intervention optimizes antiviral treatment and reduces antibiotic treatment for ED patients with suspected influenza. The secondary study endpoints are aggregate physician adherence to CDC guidelines for the treatment of influenza, antibiotic duration, hospital admission, ED return visits within 30 days for patients diagnosed with influenza and RSV, time to resolution of symptoms, return to school/work, and subsequent healthcare utilization (e.g. doctor visits) obtained through patient self-report.

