#### **F. Research Design and Methods**

This will be a prospective, patient-oriented, pilot randomized clinical trial to evaluate (in aggregate) both the use of the Flu/RSV Assay, procalcitonin, and the use of pharmacist-led education for providers in the interpretation of these test results. Children and adults <50 years of age who present to the pediatric ED of the UC Davis Medical Center with influenza-like illness (ILI), upper or lower respiratory infection (URI) will be eligible to participate.

Consented patients in the pediatric ED will be randomized into two arms: The intervention arm will receive procalcitonin with a patient specific stewardship intervention during the ED visit. The intervention will be pharmacist-led and include direct delivery to clinicians of information about interpreting test results and recommendations for antiviral-treatment for high-risk patients, and infection control precautions for patients being hospitalized with a positive RSV or influenza test and avoidance of antibiotics where not indicated. Clinician adherence to treatment guidelines with and without the educational intervention will be compared. Patients randomized to this arm will also have 1 ml of blood drawn for procalcitonin (PCT) analysis to identify bacterial infections. This sample will be taken at the time of a blood draw for standard clinical labs, or from an IV if one is in place. If no blood draw is ordered for standard of care and/or no IV is placed, patients will be given the option to consent to an extra needle stick for the purpose of research if both the clinician and patient agree to wait for the test result. Interpretation of the procalcitonin where obtained will be included in the intervention by the ED pharmacist. We will use the following protocol to guide clinicians in recommendations for antibiotic therapy. Procalcitonin will be an adjunct to guiding decision making for antibiotic use and will provide added value for both patients diagnosed with RSV and flu, as well as promote reduced antibiotic use for patients who do not have diagnosed flu or RSV and help guide appropriate treatment for those patients suspected of having LRTI. We will use a conservative protocol in both infants and older children similar to the figure attached but with a cutoff of 0.5 for recommendation of initiation of therapy in patients suspected of having LRTI.

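### The stated 80% power for the antiviral aim refers to all 100 enrolled per arm, whereas the antiviral hypothesis concerns only high-risk influenza patients, a subset of unstated size

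*Combined protocol and SAP*

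**What the plan says.** Three sections of the combined protocol and SAP describe the antiviral aim, each in different terms.

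- **Section A, hypothesis.** The intervention "will increase appropriate antiviral treatment of patients with influenza at high risk recommended to receive treatment by 20 percentage points". The population is the high-risk influenza subset.
- **Section C, sample size.** "We plan to enroll 100 patients in each arm over a 12 month period", which is said to give "80% power to detect a true 20 percentage point reduction in antibiotic use and 20 percentage point increase in adherence to guideline recommendations". The sentence ends by tying adherence to antiviral treatment. It restricts the denominator no further than enrolment.
- **Section E, endpoints.** The primary endpoint is whether the intervention "optimizes antiviral treatment and reduces antibiotic treatment for ED patients with suspected influenza". Guideline adherence appears in the next sentence: "The secondary study endpoints are aggregate physician adherence to CDC guidelines for the treatment of influenza". Section A also lists it as secondary.

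Eligibility in section C is broad. Besides suspected influenza it admits "non-specific URI for whom the clinician suspects RSV or influenza or lower respiratory infection". Section F plans an adherence comparison by arm ("Clinician adherence to treatment guidelines with and without the educational intervention will be compared") but does not say how adherence is scored or in whom. Section F also calls the trial a pilot. Section P makes the primary analysis an unstratified chi-square test with Fisher's exact test, reports the difference with a 95% CI, and adds a stratified analysis by flu status. No section gives an expected number of high-risk influenza patients, or a power for them.

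**The concern.** The 80% is the only design figure for the antiviral half of the hypothesis. It is attached to everyone enrolled and to an outcome called adherence. The hypothesis is about treatment given to a subset. Unless the outcome and denominator are the same in both places, the power statement does not describe the hypothesis.

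Two misreadings of the results could follow. A null result in the high-risk influenza subset could be taken as evidence of no effect from a trial with 80% power, when the subset may have been far too small to show one. A positive adherence result in all enrolled patients could be taken as confirming the high-risk hypothesis, which it would not test directly.

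**Working it through.** **Inputs from the plan.** 100 enrolled per arm, 80% power and a 20-point gain (section C); chi-square and Fisher tests (section P).

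**Assumptions.** Alpha is not stated for the power; two-sided 0.05 is taken from the 95% CI in section P. The control rate is not stated. Section B reports that under 40% of patients recommended for influenza treatment receive it in the ED. That is a background upper bound and not a design input, so control rates from 5% to 40% are tried. No dropout is allowed for. The number of qualifying patients per arm is not stated, so 20, 30 and 50 are illustrations.

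**Formulas** (pooled variance, equal arms, p̄ the mean of p1 and p2, d = 0.20):

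- n per arm = [1.96·√(2p̄(1−p̄)) + 0.8416·√(p1q1 + p2q2)]² / d²
- power = Φ{[d·√n − 1.96·√(2p̄(1−p̄))] / √(p1q1 + p2q2)}

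**Step 1: the plan's own figure.** At 40 vs 60%, √(2p̄(1−p̄)) = 0.7071 and √(p1q1 + p2q2) = 0.6928.

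- n = (1.3859 + 0.5831)² / 0.04 = 96.9, so 97 per arm.
- Power at 100 = Φ[(2.0 − 1.3859)/0.6928] = Φ(0.886) = 81.2%. Full enumeration gives 82.6% for chi-square and 78.7% for Fisher.

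The 80% is therefore reproduced, with all 100 per arm in the denominator.

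**Step 2: qualifying patients per arm needed for 80% power in the section A subset.** The exact columns give the first n reaching 80%.

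| Control vs intervention | Approximation | Chi-square, exact | Fisher, exact |
|---|---|---|---|
| 40 vs 60% | 97 | 97 | 102 |
| 30 vs 50% | 93 | 94 | 102 |
| 20 vs 40% | 82 | 80 | 90 |
| 10 vs 30% | 62 | 59 | 69 |
| 5 vs 25% | 49 | 44 | 55 |

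As a share of the 100 enrolled per arm, this runs from about half to nearly all by approximation or chi-square. By Fisher, at control rates of 30% and 40%, it exceeds the number enrolled.

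**Step 3: power if fewer qualify.**

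| Qualifying per arm | 40 vs 60%: approx. / chi-square / Fisher | 5 vs 25%: approx. / chi-square / Fisher |
|---|---|---|
| 50 | 51.6 / 54.3 / 46.2% | 80.9 / 85.2 / 74.8% |
| 30 | 33.8 / 35.0 / 25.7% | 58.6 / 63.3 / 43.6% |
| 20 | 23.9 / 22.2 / 14.3% | 42.2 / 44.4 / 29.9% |

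The 95% CI half-width at 40 vs 60% is 1.96·√(0.48/n): 30.4 points at 20 per arm and 19.2 points at 50.

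**Step 4: does scoring everyone test the subset hypothesis indirectly?** Suppose the subset (share s) goes from 40% to 60% and all 100 per arm are scored. The overall gain is then 20·s points plus (1−s) times any gain elsewhere.

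- No gain elsewhere, adherence there an assumed 60–90%: overall gains of 4, 6 and 10 points at s = 20, 30 and 50%, with power of 8–11%, 14–17% and 29–34%.
- An assumed 10-point gain elsewhere, from 60% to 70%: overall gains of 12, 13 and 15 points, with power of about 42%, 47% and 57%.
- A 20-point gain elsewhere from 60%: power of 83–85%.

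The all-enrolled 80% thus requires a gain of about 20 points across everyone, and a gain confined to the subset does not supply it.

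**The case against.** The strongest reply is that section C may be powering a primary outcome after all. Section E's primary endpoint concerns optimised antiviral treatment in suspected influenza, which is close to the enrolled population, and section P's primary analysis is unstratified. Optimising can cover both over- and under-treatment, which section B names as the problem, so guideline adherence in all enrolled patients is a plausible form of that endpoint. This stands. A reader might infer that the 80% belongs only to a secondary outcome because sections A and E list adherence there, but the documents do not settle that. Even so, this reading gives the section A subset no power of its own.

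A reader might also infer that the trial is shown to be underpowered for its antiviral hypothesis. The documents do not support that either. They give no qualifying share, and it need not be small: recruitment is in a pediatric ED, and section B counts children under 2 among those at particular risk. The low powers in the working are conditional on assumed numbers.

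Nor do the sections contradict each other in a figure. Both use a 20-point gain linked to recommended antiviral treatment. The fault is that the outcome and denominator differ or are undefined.

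Finally, this is a pilot, and section P reports differences with 95% CIs, so estimation in the subset would be legitimate. The plan does not say that this is the intention, and an interval calculated afterwards does not correct a power statement made beforehand.

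**Conclusion.** The point holds as a denominator and endpoint mismatch that should be fixed. The 80% is arithmetically sound for 100 scored patients per arm and could serve either the section E primary endpoint or the secondary adherence outcome. It is not shown to apply to the section A antiviral hypothesis. For that, between about half and all of those enrolled would have to qualify, depending on the control rate and test, and by Fisher at 30% or 40% control even all 100 would fall slightly short.

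Confidence in the mismatch is high, because it rests on the wording alone. The size of any shortfall is unknown: the figures rest on an assumed two-sided 0.05, control rates of 5–40% and illustrative subset numbers. The antibiotic power claim and the sample size itself are not challenged here.

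**What to change.** In section C, name the outcome and denominator to which the antiviral 80% applies, with its control rate and alpha. Then take one of two routes.

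- **If it is the section A subset:** replace the 80% with the power and 95% CI width at the expected number of high-risk influenza patients per arm. As an illustration only, 20 per arm at 40 vs 60% would read as 24% power and about ±30 points.
- **If it is all enrolled patients:** keep the 80% for that outcome, define how adherence is scored, and say whether the outcome is primary or secondary. State that the section A subset hypothesis is not separately powered and is for estimation in this pilot.

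Either way, make sections A, C and E agree.

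The cost is one recalculation and aligned wording, with no extra patients. There are two downsides. The stated antiviral power may become less favourable. A confirmed-influenza denominator also needs influenza status to be known in the standard-care arm, for which section F states no testing requirement. The all-enrolled route avoids that dependence only if adherence is scored on suspected influenza.

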#### **D. Study Timelines**

Each subject will participate actively participate in this study for 4 weeks. Additionally, after 30 days, each subject's medical record will be queried for information as described below in Section We anticipate that it will take us one year from study implementation to enroll the required number of subjects. We anticipate that the primary analyses will be completed 2 years after beginning the study.

#### **E. Study Endpoints**

[figure not shown]
The primary study endpoint is the determination of whether use of the Roche Liat Flu/RSV Assay and procalcitonin testing, as part of a stewardship intervention optimizes antiviral treatment and reduces antibiotic treatment for ED patients with suspected influenza. The secondary study endpoints are aggregate physician adherence to CDC guidelines for the treatment of influenza, antibiotic duration, hospital admission, ED return visits within 30 days for patients diagnosed with influenza and RSV, time to resolution of symptoms, return to school/work, and subsequent healthcare utilization (e.g. doctor visits) obtained through patient self-report.

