## LRTI Initial Antibiotic Use Algorithm

The second arm will be standard care.

Physicians and patients will not be blinded to test type. Tests will be performed on a real-time basis in the ED. All results will be delivered via standard of care through the EMR.

For each of these groups, data of the frequency and duration of antibiotic administration, antiviral use, adherence to evidence based guidelines for treatment of influenza, disposition, concomitant diagnoses, isolation, hospitalizations, and unscheduled return visits or readmissions within a 30 day period will be collected and compared. In addition, we will compare procalcitonin levels for patients diagnosed with RSV or influenza by the Roche LIAT in the test arm compared to those found to have evidence of bacterial infection based on chest xray, blood culture, and other ancillary tests. Where not recommended, reason for antibiotic use will be documented by the pharmacist and abstracted from chart review.

Research coordinators will contact patients and/or parents at 1 and 4 weeks after enrollment for self-reported secondary outcomes including symptom resolution, return to school/work, and follow up healthcare visits, medication adherence (to antibiotics and/or antivirals), and adverse events.

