## **I. Risks and Side Effects**

For the primary subjects we will be using identifiable protected health information, therefore there are inherent possible confidentiality risks. However, all identifiable data is accessible only to trained users and clinicians who have passwords to the EMR system. Any confidentiality risks are minimal. Identifiable information will be stored in a password-protected database,

where patients will be assigned code numbers. Medical information will be stored in a separate password-protected database, sorted by code numbers. At the completion of the data analysis all identifiers will be erased from the records.

In addition, we plan to analyze aggregate clinical practice patterns through structured data forms. No identifiable data on the clinician will be recorded on research forms. No information on staff members will be recorded, thus we expect no risk to clinician or staff members' employment.

This study also presents several possible physical risks to the subjects randomized to Arm 1 of this study. Risks related to venipuncture for those who consent to an extra needle stick include pain, bruising, bleeding, or infection at the blood drawing site. The total volume of blood obtained for this study in the ED will not exceed 1 mL.

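### The antibiotic endpoint and its analysis count any antibiotic use in all patients, so the hypothesis's limit to conditions that do not respond to antibiotics is lost and an antibiotic withheld in bacterial infection scores as success

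*Combined protocol and SAP*

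**What the plan says.** The aim is stated narrowly in two places.

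- Section A (Objective), hypothesis: "reduced antibiotic treatment by 20 percentage points compared to the control group for antibiotic non-responsive conditions including ILI and nonspecific URI".
- Section F (Research Design and Methods), content of the pharmacist-led intervention: "avoidance of antibiotics where not indicated".

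The outcome is stated broadly in three.

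- Section E (Study Endpoints): the question is whether the intervention "optimizes antiviral treatment and reduces antibiotic treatment for ED patients with suspected influenza".
- Section C (Study Population): 100 per arm is said to give 80% power for a 20-point fall in antibiotic use, with no condition attached.
- Section P (Statistical Analysis): the primary comparison is an unstratified Chi-square (and Fisher) test of proportions by arm. The only stratifier is flu status.

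Patients with bacterial disease can be enrolled. Section C admits those "for whom the clinician suspects RSV or influenza or lower respiratory infection (with or without ordering a chest xray").

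Evidence of bacterial infection has one planned use. In the text under the LRTI algorithm, procalcitonin levels in patients with RSV or influenza are compared with those of "those found to have evidence of bacterial infection based on chest xray, blood culture, and other ancillary tests". The same text reviews antibiotics in one direction only: "Where not recommended, reason for antibiotic use will be documented by the pharmacist and abstracted from chart review".

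**The concern.** Antivirals are to be optimised, which implies a standard of appropriateness. Antibiotics are only to be reduced. The intervention uses procalcitonin to inform decisions both for and against starting antibiotics in suspected lower respiratory infection, so a lower antibiotic rate mixes two things: antibiotics that were not needed, and antibiotics that were. The endpoint gives both the same credit. No planned table would let a reader separate them, although that is the distinction the hypothesis draws.

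Section I opens its account of physical harm with "This study also presents several possible physical risks to the subjects randomized to Arm 1 of this study" and then describes only venipuncture. An intervention designed to change antibiotic decisions also carries the risk that a bacterial infection goes untreated, and section I does not mention it.

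**Working it through.** **1. The plan's own figure.** Inputs: 100 per arm, 80% power and a 20-point difference (section C). The control antibiotic rate and alpha are not stated. I assume two-sided 0.05, in line with the 95% CI in section P, and vary the control rate. With the pooled normal approximation,

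n = [1.960·√(2p̄(1−p̄)) + 0.842·√(p₁(1−p₁)+p₂(1−p₂))]² / (p₁−p₂)².

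For 60% v 40%: [1.960·0.7071 + 0.842·0.6928]² / 0.04 = 97 per arm; power at 100 per arm is 81.2%. For 50% v 30%: n = 93, power 82.8%. For 40% v 20%: n = 82, power 87.6%. The stated size is reproduced, and it rests on plain antibiotic use in all 100 patients per arm.

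**2. How a reduction splits.** Let b be the share with bacterial infection, equal in expectation across arms by randomisation. Let Δ_B and Δ_N be the control-minus-intervention differences in the proportion treated among patients with and without bacterial infection. Then

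overall reduction = (1−b)·Δ_N + b·Δ_B.

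The second term is the part due to withheld treatment in bacterial infection. It depends on the difference between arms: if both arms leave the same proportion untreated, it is zero.

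**3. Size.** Neither b nor Δ_B is in the documents; these are assumptions.

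| b | Δ_B = 25 points | Δ_B = 50 points |
|---|---|---|
| 10% | 2.5 points | 5 points |
| 20% | 5 points | 10 points |
| 30% | 7.5 points | 15 points |

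Against the 20-point target this is 12.5% to 75%.

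**4. A full example (all rates assumed).** Take b = 20%, with treatment falling from 95% to 55% in bacterial patients and from 50% to 35% in the rest.

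- Control: 0.8·50 + 0.2·95 = 59%.
- Intervention: 0.8·35 + 0.2·55 = 39%.
- Reduction: 20 points, of which 0.2·40 = 8 come from bacterial patients and 0.8·15 = 12 from the others.

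The trial would have 81% power to declare this result, and the planned analysis would report it no differently from 20 points of unneeded antibiotics.

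**5. Can the other outcomes reveal it?** Assume an admission or return rate of 5–10%. The 95% half-width for a difference at 100 per arm is 1.96·√(2p(1−p)/100): 6.0 points at 5% and 8.3 points at 10%. Differences of a few points would not show.

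**6. Would a bacterial-subgroup test help?** With 10 to 20 such patients per arm, power to detect a fall from 95% to 70% treated is about 30% to 55% (normal approximation, rough at these sizes). Any such comparison is descriptive.

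**The case against.** **The plan does not intend every avoided antibiotic to be a success.** Sections A and F both say otherwise, and a reader of section E alone might infer more than the documents support. This stands, and it narrows the point: the intended limit exists but does not reach sections C, E and P. Section A also sets the limit by syndrome (ILI, nonspecific URI), so carrying it over unchanged would still leave in an ILI patient who has a bacterial infection.

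**Harm is monitored.** A reader might infer that the trial has no safety check. It has several: by arm, concomitant diagnoses, disposition, and "hospitalizations, and unscheduled return visits or readmissions within a 30 day period will be collected and compared", plus adverse events asked about at 1 and 4 weeks. Concomitant diagnoses come closest to what is needed. None of these is linked to whether an antibiotic was given, and section E words the return-visit endpoint for patients diagnosed with influenza and RSV.

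**The size could be overstated.** It is tempting to count untreated bacterial patients in the intervention arm and subtract them from the reduction. That assumes the control arm misses none. Only the between-arm difference contributes.

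**Bacterial evidence is not a clean classifier.** Chest x-ray is optional, no section requires cultures, clinicians are unblinded, and test ordering follows randomisation and may be changed by the intervention. A split by this evidence is therefore not a protected randomised comparison. Nor should evidence arising weeks later be scored against the decision at the ED visit. Both objections stand and shape the fix.

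**Some material cannot be seen.** The LRTI algorithm figure and the consent pages are not available, so neither the safeguards in the algorithm nor disclosure of this risk to patients can be judged. Only the silence of section I can be verified.

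**Conclusion.** The concern holds in this form: sections C, E and P measure any antibiotic use in all enrolled patients, whereas section A's hypothesis and section F's intervention concern antibiotics that are not needed. Following the plan as written, a reduction cannot be divided into antibiotics rightly and wrongly avoided. The part at stake is b·Δ_B: 2.5 to 15 points for assumed bacterial shares of 10–30% and drops of 25–50 points, and zero if the arms do not differ in how they treat bacterial patients. Those inputs are assumptions.

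The documents do not show that the intervention causes under-treatment, that harm goes unmonitored, or that the sample size is wrong. The finding is that the planned analysis could not tell a beneficial reduction from a partly harmful one.

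**What to change.** 1. **Sections E and P.** Carry over the section A limit by also reporting antibiotic use without documented bacterial infection, by arm. Keep all randomised patients in the denominator. Restricting to patients without bacterial infection would instead cut power at 60% v 40% from 81% to 77%, 72% or 66% for assumed bacterial shares of 10%, 20% or 30%.
2. **Section P.** Report by arm, over all randomised patients with difference and 95% CI, the number with bacterial evidence from the index visit who received no antibiotic. Evidence means x-ray, cultures taken at that visit and ancillary tests. Exclude procalcitonin, which is drawn only in the intervention arm. Classify blind to arm. List bacterial diagnoses arising later within 30 days separately.
3. **Section P.** Report x-ray and culture testing rates by arm, and label any split by bacterial evidence as descriptive, because testing is optional and follows randomisation.
4. **Interpretation.** State that a reduction will be described as beneficial only alongside these figures. This adds no hypothesis test.
5. **Section I.** Add the risk that a bacterial infection goes untreated.

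**Cost.** Wording in E, P and I, and chart abstraction of the same evidence in the control arm, which the current text does not clearly provide for. Counts will be small: even no such patient in 100 leaves an exact two-sided 95% upper limit of 1 − 0.025^(1/100) = 3.6%. The result is an estimate with a wide interval, which suits a pilot.
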